8.1 TRIAL APPROVAL, PATIENT INFORMATION, INFORMED CONSENT

This trial will be initiated only after all required legal documentation has been reviewed and approved by the respective IRB/IEC and CA according to national and international regulations. The same applies for the implementation of changes introduced by amendments. Prior to patient participation in the trial, written informed consent must be obtained from each patient (or the patient's legally accepted representative) according to ICH-GCP and to the regulatory and legal requirements of the participating country. Each signature must be personally dated by each signatory and the informed consent and any additional patient-information form retained by the investigator as part of the trial records. A signed copy of the informed consent and any additional patient information must be given to each patient or the patient's legally accepted representative."

The investigator or delegate must give a full explanation to trial patients based on the patient information form. A language understandable to the patient should be chosen, technical terms and expressions avoided, if possible.

The patient must be given sufficient time to consider participation in the trial. The investigator or delegate obtains written consent of the patient's own free will with the informed consent form after confirming that the patient understands the contents. The investigator or [redacted] delegate must sign (or place a seal on) and date the informed consent form. If a trial collaborator has given a supplementary explanation, the trial collaborator also signs (or places a seal on) and dates the informed consent.

Re-consenting may become necessary when new relevant information becomes available and should be conducted according to the sponsor's instructions.

The consent and re-consenting process should be properly documented in the source documentation.

8.2 DATA QUALITY ASSURANCE

A risk-based approach is used for trial quality management. It is initiated by the assessment of critical data and processes for trial subject protection and reliability of the results as well as identification and assessment of associated risks. An Integrated Quality and Risk Management Plan documents the rationale and strategies for risk management during trial conduct including monitoring approaches, vendor management and other processes focusing on areas of greatest risk.

Continuous risk review and assessment may lead to adjustments in trial conduct, trial design or monitoring approaches.

A quality assurance audit/inspection of this trial may be conducted by the sponsor, sponsor's designees, or by IRB / IEC or by regulatory authorities. The quality assurance auditor will have access to all medical records, the investigator's trial-related files and correspondence, and the informed consent documentation of this clinical trial.

8.3 RECORDS

CRFs for individual patients will be provided by the sponsor. For drug accountability, refer to Section [4.1.12](#).

8.3.1 Source documents

In accordance with regulatory requirements, the investigator should prepare and maintain adequate and accurate source documents and trial records that include all observations and other data pertinent to the investigation on each trial patient. Source data as well as reported data should follow the "ALCOA principles" and be **attributable, legible, contemporaneous, original and accurate**. Changes to the data should be traceable (audit trail).

Data reported on the CRF must be consistent with the source data or the discrepancies must be explained.

The current medical history of the patient may not be sufficient to confirm eligibility for the trial and the investigator may need to request previous medical histories and evidence of any diagnostic tests. In this case, the investigator must make at least one documented attempt to retrieve previous medical records. If this fails, a verbal history from the patient, documented in their medical records, would be acceptable.

Copies of source documents necessary for tumour assessment will be provided to an authorised vendor. Before sending or uploading those copies, the investigator must ensure that all patient identifiers (e.g. patient's name, initials, address, phone number, social security number) have properly been removed or redacted from any copy of the patients' source documents.

If the patient is not compliant with the protocol, any corrective action e.g. re-training must be documented in the patient file.

For the CRF, data must be derived from source documents, for example:

- Patient identification: gender, year of birth (in accordance with local laws and regulations)
- Patient participation in the trial (substance, trial number, patient number, date patient was informed)
- Dates of patient's visits, including dispensing of trial medication
- Medical history (including trial indication and concomitant diseases, if applicable)
- Medication history
- Adverse events and outcome events (onset date (mandatory), and end date (if available))
- Serious adverse events (onset date (mandatory), and end date (if available))
- Concomitant therapy (start date, changes)
- Originals or copies of laboratory results and other imaging or testing results, with proper documented medical evaluation (in validated electronic format, if available)
- Completion of patient's participation in the trial" (end date; in case of premature discontinuation document the reason for it).
- Prior to allocation of a patient to a treatment into a clinical trial, there must be documented evidence in the source data (e.g. medical records) that the trial participant meets all inclusion criteria and does not meet any exclusion criteria. The absence of records (either medical records, verbal documented feedback of the patient or testing conducted specific for a protocol) to support inclusion/exclusion criteria does not make the patient eligible for the clinical trial.

8.3.2 Direct access to source data and documents

The investigator /institution will allow site trial-related monitoring, audits, IRB / IEC review and regulatory inspections. Direct access must be provided to the CRF and all source documents/data, including progress notes, copies of laboratory and medical test results, which must be available at all times for review by the CRA, auditor and regulatory inspector (e.g. FDA). They may review all CRFs and informed consents. The accuracy of the data will be verified by direct comparison with the source documents described in Section [8.3.1](#). The sponsor will also monitor compliance with the protocol and GCP.

8.3.3 Storage period of records

Trial site(s):

The trial site(s) must retain the source and essential documents (including ISF) according to contract or the local requirements valid at the time of the end of the trial (whatever is longer).

Sponsor:

The sponsor must retain the essential documents according to the sponsor's SOPs.

8.4 EXPEDITED REPORTING OF ADVERSE EVENTS

BI is responsible to fulfil their legal and regulatory reporting obligation in accordance with regulatory requirements.

Exemptions from expedited reporting are described in Section [5.2.9.2.4](#).

8.5 STATEMENT OF CONFIDENTIALITY AND PATIENT PRIVACY

Data protection and data security measures are implemented for the collection, storage and processing of patient data in accordance with the principles 7 and 12 of the World Health Organisation (WHO) GCP handbook.

Individual patient data obtained as a result of this trial is considered confidential and disclosure to third parties is prohibited with the following exceptions:

Personalised treatment data may be given to the patient's personal physician or to other appropriate medical personnel responsible for the patient's welfare. Data generated at the site as a result of the trial need to be available for inspection on request by the participating physicians, the sponsor's representatives, by the IRB / IEC and the regulatory authorities.

8.5.1 Collection, storage and future use of biological samples and corresponding data

Measures are in place to comply with the applicable rules for the collection, biobanking and future use of biological samples and clinical data, in particular

- Sample and data usage has to be in accordance with the separate biobanking informed consent
- The BI-internal facilities storing biological samples from clinical trial participants as well as the external banking facility are qualified for the storage of biological samples collected in clinical trials
- An appropriate sample and data management system, incl. audit trail for clinical data and samples to identify and destroy such samples according to ICF is in place
- A fit for the purpose documentation (biomarker proposal, analysis plan and report) ensures compliant usage
- A fit for purpose approach will be used for assay/equipment validation depending on the intended use of the biomarker data
- Samples and/or data may be transferred to third parties and other countries as specified in the biobanking ICF

8.6 TRIAL MILESTONES

The **start of the trial** is defined as the date when the first patient in the whole trial signs informed consent.

The **end of the trial** is defined as the date of the last visit of the last patient in the whole trial ("Last Patient Completed").

The “**Last Patient Last Treatment**” (LPLT) date is defined as the date on which the last patient in the whole trial is administered the last dose of trial treatment (as scheduled per protocol or prematurely). Individual investigators will be notified of suspected unexpected serious adverse reactions (SUSARs) occurring with the trial medication until 30 days after LPLT at their site. **Early termination of the trial** is defined as the premature termination of the trial due to any reason before the end of the trial as specified in this protocol.

Temporary halt of the trial is defined as any unplanned interruption of the trial by the sponsor with the intention to resume it.

Suspension of the trial is defined as an interruption of the trial based on a Health Authority request.

8.7 ADMINISTRATIVE STRUCTURE OF THE TRIAL

The trial is sponsored by Boehringer Ingelheim.

A Coordinating Investigator is responsible to coordinate investigators at the different sites participating in this trial. Tasks and responsibilities are defined in a contract.

A SMC composed of participating investigators and members of the BI trial team will be established to review individual and aggregated safety and efficacy data at regular intervals to determine the safety profile, risk/benefit ratio, recommend next dose level/does escalation/de-escalation/modification/next cohort size, and appropriateness of further enrolment.

Details of the SMC responsibilities and procedures are described in the SMC charter.

Relevant documentation on the participating (Principal) Investigators (e.g. their curricula vitae) will be filed in the ISF. The investigators will have access to the BI clinical trial portal (Clinergize) to facilitate document exchange and maintain electronic ISF.

BI has appointed a Clinical Trial Leader (CT Leader), responsible for coordinating all required activities, in order to

- manage the trial in accordance with applicable regulations and internal SOPs,
- direct the clinical trial team in the preparation, conduct, and reporting of the trial,
- ensure appropriate training and information of Clinical Trial Managers (CT Managers), Clinical Research Associates (CRAs), and investigators of participating countries.

The organisation of the trial in the participating countries will be performed by the respective local or regional BI-organisation (Operating Unit, OPU) in accordance with applicable regulations and BI SOPs, or by a CRO with which the responsibilities and tasks will have been agreed and a written contract filed before initiation of the clinical trial.

Data Management will be done by BI or a vendor according to BI SOPs.
Statistical Evaluation will be done by BI according to BI SOPs.

Tasks and functions assigned in order to organise, manage, and evaluate the trial are defined according to BI SOPs. A list of responsible persons and relevant local information can be found in the ISF.

A central laboratory service, a central imaging collection service, and an IRT vendor will be used in this trial. Details will be provided in the IRT Manual and Central Laboratory Manual, available in the ISF.

10. APPENDICES

10.1 IMMUNE-RELATED ADVERSE EVENTS OF SPECIAL INTEREST

Table 10.1: 1 Immune-related adverse events of special interest

This table defines immune-related AEs that must be reported as AESIs if they occur after exposure to BI 754091.

Immune-related adverse events of special interest
Pneumonitis (report as AESI if an irAE is \geq Grade 2)

• Acute interstitial pneumonitis• Interstitial lung disease• Pneumonitis
Colitis (report as AESI if an irAE is \geq Grade 2 or any grade resulting in dose modification or use of systemic steroids to treat the AE)

• Intestinal obstruction• Colitis• Colitis microscopic• Enterocolitis• Enterocolitis haemorrhagic• Gastrointestinal perforation• Necrotizing colitis• Diarrhea
Endocrine (report as AESI if an irAE is \geq Grade 3 or \geq Grade 2 and resulting in dose modification or use of systemic steroids to treat the AE)

• Adrenal insufficiency• Hyperthyroidism• Hypophysitis• Hypopituitarism• Hypothyroidism• Thyroid disorder• Thyroiditis• Hyperglycaemia, if \geq Grade 3 and associated with ketosis or metabolic acidosis
Endocrine (report as AESI for any grade)

• Type 1 diabetes mellitus (if new onset)

Immune-related adverse events of special interest

Hematologic (report as AESI if an irAE is \geq Grade 3 or any grade resulting in dose modification or use of systemic steroids to treat the AE)

- Autoimmune haemolytic anaemia
- Aplastic anaemia
- Thrombotic thrombocytopenic purpura
- Idiopathic (or immune) thrombocytopenia purpura
- Disseminated intravascular coagulation
- Haemolytic-uraemic syndrome
- Any Grade 4 anaemia regardless of underlying mechanism

Hepatic (report as AESI if an irAE is \geq Grade 2, or any grade resulting in dose modification or use of systemic steroids to treat the AE)

- Hepatitis
- Autoimmune hepatitis
- Transaminase elevations (ALT and/or AST)

Infusion Reactions (report as AESI for any grade)

- Allergic reaction
- Anaphylaxis
- Cytokine release syndrome
- Serum sickness
- Infusion reactions
- Infusion-like reactions

Neurologic (report as AESI for any grade)

- Autoimmune neuropathy
- Guillain-Barre syndrome
- Demyelinating polyneuropathy
- Myasthenic syndrome

Ocular (report as AESI if an irAE is \geq Grade 2 or any grade resulting in dose modification or use of systemic steroids to treat the AE)

- Uveitis
- Iritis

Immune-related adverse events of special interest

Renal (report as AESI if an irAE is \geq Grade 2)

- Nephritis
- Nephritis autoimmune
- Renal failure
- Renal failure acute
- Creatinine elevations (report as an irAE if \geq Grade 3 or any grade resulting in dose modification or use of systemic steroids to treat the AE)

Skin (report as AESI for any grade)

- Dermatitis exfoliative
- Erythema multiforme
- Stevens-Johnson syndrome
- Toxic epidermal necrolysis

Skin (report as AESI if an irAE is \geq Grade 3)

- Pruritus
- Rash
- Rash generalized
- Rash maculopapular
- Any rash considered clinically significant in the physician's judgment

Other (report as AESI for any grade)

- Myocarditis
- Pancreatitis
- Pericarditis
- Any other Grade 3 event that is considered immune-related by the physician

10.2 MANAGEMENT OF IMMUNE-RELATED ADVERSE EVENTS (PART II ONLY)

Management of immune-related adverse event toxicities associated with anti-PD-1 mAbs are presented below. **BI 754091 should be permanently discontinued for Grade 3-4 pneumonitis, Grade 3-4 adrenal insufficiency, Grade 4 diabetes mellitus, any grade encephalitis, Grade 4 hypophysitis, Grade 4 rash, Grade 3-4 or recurrent colitis of any grade, any recurrent Grade 3-4 AE, transaminase increased >5 times ULN or total bilirubin >3 times ULN (unless unequivocally attributable to another cause), inability to taper steroids to 10 mg or less prednisone or equivalent within 12 weeks, or persistent Grade 2-3 AEs that do not recover to Grade 1 or less within 12 weeks.**

- Pneumonitis:
 - For Grade 2 events, treat with systemic corticosteroids. When symptoms improve to Grade 1 or less, steroid taper should be started and continued over no less than 28 days.
 - Add prophylactic antibiotics for opportunistic infections in the case of prolonged steroid administration.
 - For Grade 3-4 events immediately treat with i.v. steroids. Administer additional anti-inflammatory measures, as needed.
 - BI 754091 should be permanently discontinued for Grade 3-4 pneumonitis, inability to taper steroids to 10 mg or less prednisone or equivalent within 12 weeks, or persistent Grade 2 AEs that do not recover to Grade 1 or less within 12 weeks.
- Diarrhoea/Colitis:

Subjects should be carefully monitored for signs and symptoms of enterocolitis (such as diarrhoea, abdominal pain, blood or mucus in stool, with or without fever) and of bowel perforation (such as peritoneal signs and ileus).

 - All subjects who experience diarrhoea/colitis should be advised to drink liberal quantities of clear fluids. If sufficient oral fluid intake is not feasible, fluid and electrolytes should be substituted via i.v. infusion. For Grade 2 or higher diarrhoea, consider GI consultation and endoscopy to confirm or rule out colitis.
 - For Grade 2 diarrhoea/colitis that persists greater than 3 days, administer oral corticosteroids.
 - For Grade 3 or 4 diarrhoea that persists >1 week, treat with i.v. steroids followed by high-dose oral steroids.
 - For Grade 3 or 4 colitis, or recurrent colitis of any grade, permanently discontinue BI 754091, and immediately treat with i.v. steroids followed by high-dose oral steroids.
 - When symptoms improve to Grade 1 or less, steroid taper should be started and continued over no less than 28 days.
 - BI 754091 should be permanently discontinued for Grade 3-4 or recurrent colitis of any grade, inability to taper steroids to 10 mg or less prednisone or equivalent within 12 weeks, or persistent Grade 2-3 AEs that do not recover to Grade 1 or less within 12 weeks.
- Type 1 diabetes mellitus (if new onset, including diabetic ketoacidosis) Grade 3, or \geq Grade 3 hyperglycaemia, if associated with ketosis (ketonuria) or metabolic acidosis

Proprietary confidential information © 2019 Boehringer Ingelheim International GmbH or one or more of its affiliated companies

- For Type 1 diabetes mellitus Grade 3-4 or Grade 3-4 hyperglycaemia
 - Insulin replacement therapy is recommended for Type I diabetes mellitus and for Grade 3-4 hyperglycaemia associated with metabolic acidosis or ketonuria.
 - Evaluate subjects with serum glucose and a metabolic panel, urine ketones, glycosylated haemoglobin, and C-peptide.
- BI 754091 should be permanently discontinued for Grade 4 diabetes mellitus, any recurrent Grade 3 AE or persistent Grade 2-3 AE that does not recover to Grade 1 or less within 12 weeks.
- Hypophysitis:
 - For Grade 2 events, treat with corticosteroids. When symptoms improve to Grade 1 or less, steroid taper should be started and continued over no less than 28 days. Replacement of appropriate hormones may be required as the steroid dose is tapered.
 - For Grade 3 events, treat with an initial dose of i.v. corticosteroids followed by oral corticosteroids. When symptoms improve to Grade 1 or less, steroid taper should be started and continued over no less than 28 days. Replacement of appropriate hormones may be required as the steroid dose is tapered.
 - For Grade 4 events, permanently discontinue BI 754091, and treat with an initial dose of i.v. corticosteroids followed by oral corticosteroids. When symptoms improve to Grade 1 or less, steroid taper should be started and continued over no less than 28 days. Replacement of appropriate hormones may be required as the steroid dose is tapered.
 - BI 754091 should be permanently discontinued for Grade 4 hypophysitis, any recurrent Grade 3 AE, inability to taper steroids to 10 mg or less prednisone or equivalent within 12 weeks, or persistent Grade 2-3 AEs that do not recover to Grade 1 or less within 12 weeks.
- Hyperthyroidism or Hypothyroidism:

Thyroid disorders can occur at any time during treatment. Monitor subjects for changes in thyroid function (at the start of treatment, periodically during treatment, and as indicated based on clinical evaluation) and for clinical signs and symptoms of thyroid disorders.

 - For Grade 2 hyperthyroidism events (and Grade 3-4 hypothyroidism):
 - In hyperthyroidism, nonselective beta-blockers (e.g., propranolol) are suggested as initial therapy.
 - In hypothyroidism, thyroid hormone replacement therapy, with levothyroxine or liothyronine, is indicated per standard of care.
 - For Grade 3-4 hyperthyroidism
 - Treat with an initial dose of i.v. corticosteroid followed by oral corticosteroids. When symptoms improve to Grade 1 or less, steroid taper should be started and continued over no less than 28 days. Replacement of appropriate hormones may be required as the steroid dose is tapered.
 - BI 754091 should be permanently discontinued for any recurrent Grade 3-4 AE, inability to taper steroids to 10 mg or less prednisone or equivalent within 12 weeks, or persistent Grade 2-3 AEs that do not recover to Grade 1 or less within 12 weeks.

Proprietary confidential information © 2019 Boehringer Ingelheim International GmbH or one or more of its affiliated companies

- Hepatic:
 - For Grade 2 events, monitor liver function tests more frequently until returned to baseline values (consider weekly).
 - Treat with i.v. or oral corticosteroids
 - For Grade 3-4 events, treat with i.v. corticosteroids for 24 to 48 hours.
 - When symptoms improve to Grade 1 or less, a steroid taper should be started and continued over no less than 28 days.
 - BI 754091 should be permanently discontinued for any recurrent Grade 3-4 AE, transaminase increases >5 times ULN or total bilirubin >3 times ULN (unless unequivocally attributable to another cause), inability to taper steroids to 10 mg or less prednisone or equivalent within 12 weeks, or persistent Grade 2-3 AEs that do not recover to Grade 1 or less within 12 weeks.
- Renal failure or nephritis:
 - For Grade 2 events, treat with corticosteroids.
 - For Grade 3-4 events, treat with systemic corticosteroids.
 - When symptoms improve to Grade 1 or less, steroid taper should be started and continued over no less than 28 days.
 - BI 754091 should be permanently discontinued for any recurrent Grade 3-4 AE, inability to taper steroids to 10 mg or less prednisone or equivalent within 12 weeks, or persistent Grade 2-3 AEs that do not recover to Grade 1 or less within 12 weeks.
- Adrenal insufficiency:
 - BI 754091 should be permanently discontinued for Grade 3-4 adrenal insufficiency or persistent Grade 2 AEs that do not recover to Grade 1 or less within 12 weeks.
- Rash:
 - BI 754091 should be permanently discontinued for Grade 4 rash, any recurrent Grade 3 AE or persistent Grade 2-3 AEs that do not recover to Grade 1 or less within 12 weeks.
- Encephalitis:
 - BI 754091 should be permanently discontinued for any grade encephalitis.
- Infusion reactions:

Signs and symptoms usually develop during or shortly after drug infusion and generally resolve completely within 24 hours of completion of infusion.

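### Appendix 10.2 (Part II guidance): Grade 3-4 diarrhoea not classed as colitis has a steroid recommendation only after 1 week, against 3 days at Grade 2

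*Protocol*

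**What the plan says.** The Diarrhoea/Colitis part of protocol Appendix 10.2 contains three steroid lines and one work-up line.

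- Grade 2 diarrhoea or colitis: "For Grade 2 diarrhoea/colitis that persists greater than 3 days, administer oral corticosteroids".
- Grade 3-4 diarrhoea: "For Grade 3 or 4 diarrhoea that persists >1 week, treat with i.v. steroids followed by high-dose oral steroids".
- Grade 3-4 colitis, or recurrent colitis of any grade: "permanently discontinue BI 754091, and immediately treat with i.v. steroids followed by high-dose oral steroids".
- Work-up: "For Grade 2 or higher diarrhoea, consider GI consultation and endoscopy to confirm or rule out colitis". This is optional and has no deadline.

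Protocol 5.2.9.1.4 describes Appendix 10.2 as recommendations. Table 1.4.2: 1 names those recommendations, together with investigators' experience, as part of the mitigation for immune-related risk.

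**The concern.** The two diarrhoea triggers run in the wrong order by severity. A site that follows the text literally would start oral steroids on day 4 for Grade 2 diarrhoea. For Grade 3-4 diarrhoea that began abruptly and has not been called colitis, it would wait until day 8. During those days colitis may simply be unconfirmed, because the only step that would move the patient to the immediate-treatment line is the optional work-up. The same part of Appendix 10.2 asks sites to watch for enterocolitis and bowel perforation, so the delay falls where the protocol itself sees risk. What is at stake is the safety of individual Part II patients.

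**Working it through.** The plan gives no figure to reproduce. The check compares the day thresholds and looks for any other rule that would trigger steroids sooner.

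**Inputs (Appendix 10.2).** Grade 2 trigger: more than 3 days. Grade 3-4 diarrhoea trigger: more than 1 week, taken as 7 days. Grade 3-4 or recurrent colitis: immediate.

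**Convention (assumed).** Day 1 is the first day at Grade 2 or higher. A trigger of more than n days is first met on day n + 1.

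**Earliest recommended steroid day.**
- Grade 2: 3 + 1 = day 4.
- Abrupt Grade 3-4 diarrhoea: 7 + 1 = day 8.
- Gap: 8 - 4 = 4 days (days 4, 5, 6 and 7).

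**Worsening after k days at Grade 2, with k = 1, 2 or 3.** The text does not say whether persistence counts from the onset of diarrhoea or restarts at the new grade.
- Counted from onset: day 8, so the gap is 4 days.
- Restarted at Grade 3-4: that grade begins on day k + 1 and the trigger is met on day k + 8. The gap is (k + 8) - 4 = k + 4 days.

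| Path | Earliest steroid day | Days without a recommendation while Grade 2 has one |
|---|---|---|
| Abrupt Grade 3-4 diarrhoea, not classed as colitis | 8 | 4 |
| 1 day at Grade 2, then Grade 3-4 | 8 or 9 | 4 or 5 |
| 2 days at Grade 2, then Grade 3-4 | 8 or 10 | 4 or 6 |
| 3 days at Grade 2, then Grade 3-4 | 8 or 11 | 4 or 7 |
| More than 3 days at Grade 2, then Grade 3-4 | 4 (oral line already met) | 0 |
| Grade 3-4 or recurrent colitis | at once | 0 |

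**Could the Grade 2 line be read to include higher grades?** Not readily. The work-up line in the same list says Grade 2 or higher when it means that, and Grade 3-4 diarrhoea has its own line.

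**Does another section set an earlier trigger?** None does.
- Protocol 4.2.2.1 accepts immunosuppression for product-related events.
- Protocol 4.2.1.1 refers diarrhoea treatment to institutional standards.
- Protocol 4.1.6 interrupts dosing for a DLT and sets retreatment conditions.
- Protocol 4.1.7 defines DLTs.
- Table 10.1: 1 and protocol 5.2.9.2.2 require immune-related diarrhoea of Grade 2 or higher to be reported within 24 hours.

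None of these names a day on which steroids should start.

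**After the fix.** With a trigger of more than 3 days counted from the first day at Grade 2 or higher, the earliest day is 4 on every diarrhoea path, and 4 - 4 = 0.

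**The case against.** The strongest reply is that passive waiting is unlikely in practice. Appendix 10.2 is advisory. The institutional-standards wording in 4.2.1.1 is mandatory, although it sits in an item on pre-medication. Investigators are described as experienced. Diarrhoea of Grade 3 or higher is a potential DLT that interrupts dosing, and a Grade 3 immune-related event escapes DLT status only if it resolves within 2 weeks with immunosuppression, which presupposes active treatment. All of this stands and lowers the weight of the point. It does not change the order of the two written triggers.

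A second reply is that the wait is deliberate: protocol 1.2.1 lists diarrhoea among the commonest adverse events of BI 836880, so its cause needs sorting out before high-dose steroids. That is plausible, though the documents do not say so. The same uncertainty exists at Grade 2, where the wait is shorter. It therefore does not explain a longer wait at the higher grade, or why not even oral steroids are recommended meanwhile.

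A reader might also infer that the line is a drafting slip because it is the only one of eight steroid lines for Grade 3 or higher with a waiting period (pneumonitis, diarrhoea, colitis, hypophysitis Grade 3, hypophysitis Grade 4, hyperthyroidism, hepatic, renal). The pneumonitis line, for example, says "For Grade 3-4 events immediately treat with i.v. steroids". The count is correct but weak evidence. Diarrhoea/colitis is also the only one of five Grade 2 steroid lines with a wait (the others are pneumonitis, hypophysitis, hepatic and renal), so the appendix treats diarrhoea differently at both grades.

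**Conclusion.** The inversion is real but narrow. For abrupt Grade 3-4 diarrhoea not classed as colitis it lasts 4 days. After 1 to 3 days at Grade 2 it lasts 4 days, or 5 to 7 if the clock restarts. Elsewhere it is zero. These figures rest on the day-counting convention above and on a site following the written triggers.

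Three stronger readings are not supported.

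- *All severe diarrhoea or colitis is undertreated for 4 days.* Colitis of Grade 3-4, or recurrent, is treated at once, and the 4-day figure is certain only for abrupt onset.
- *The delay distorts DLT counts and hence the MTD.* Waiting until day 8 would use 7 of the 14 days in the Grade 3 exemption of 4.1.7 if both clocks start at onset. The documents give neither a frequency of such events for the combination nor a time to resolution, and earlier steroids are allowed, so no effect on the MTD, the primary endpoint or the analysis follows.
- *High-dose i.v. steroids must start immediately.* Removing the inversion does not require that, and the timing of the i.v. step before colitis is confirmed is a clinical judgement.

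Part II expects about 15 patients (protocol 7.6), and no number affected can be estimated. This is a minor patient-safety correction.

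**What to change.** Make the steroid trigger for Grade 3-4 diarrhoea no later than the Grade 2 trigger, and state that the count runs from the first day at Grade 2 or higher.

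The minimum change is to widen the Grade 2 line, for example: *give corticosteroids for diarrhoea or colitis of Grade 2 or higher once it has lasted more than 3 days, counted from the first day at Grade 2 or higher.* The existing Grade 3-4 line can then stay as the later step up to i.v. treatment. Alternatively, the sponsor's clinical team may bring the i.v. step itself forward to at most 3 days. The immediate line for colitis is unchanged.

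The cost is a small text edit in Appendix 10.2, with no change to design, sample size, data collection, DLT rules or analysis. The clinical downside is that some patients whose severe diarrhoea is not immune-mediated would receive steroids earlier. The optional work-up limits this only where it is done promptly.
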